8.3 Other Secondary Outcomes

The protocol defines a number of secondary endpoints in addition to the two key endpoints described in section 8.2 above. These analyses will be carried out for the final report. Selected secondary endpoints may also be analyzed for interim monitoring reports, to help evaluate the safety and efficacy of the investigational agent.

Below, the secondary outcomes from section 4.2.2 of the protocol are cited, with a short description of the analysis methods. For each outcome, the treatment group comparisons will be stratified by disease severity at study entry and by site pharmacy, as described in section 3 under "stratification".

- Time to discharge for the initial hospitalization. Treatment groups will be compared using time-to-event methods that take into account the competing risk of death, similar to the analyses for time to sustained recovery described in section 8.1.
 - Hospital readmissions will be summarized using methods for recurrent events (i.e. those who are readmitted will re-enter the risk set).⁹
- Days alive outside of a short-term acute care hospital up to day 90. For this analysis, the "last-off" method will be used, i.e., days from the latest hospital discharge to day 90 will be counted. A person who dies within 90 days will be assigned a value of 0, consistent with the approach taken in trials of intensive care-based interventions. We will present

the median days by group and test the hypothesis of no difference between arms with a Wilcoxon rank sum test.

- For interim analyses, only participants who have reached Day 90 (administrative follow-up for those who died) will be included, to avoid bias. Alternatively, a shorter time period may be used.
- Pulmonary+ and pulmonary ordinal outcomes on Days 1-7, and the pulmonary ordinal outcome on Days 14 and 28. The proportion of participants in each category of the pulmonary and pulmonary+ outcomes will be summarized over time (both outcomes at days 1-7, the pulmonary outcome also at Days 14 and 28); at each of those days, treatment groups will be compared using proportional odds models as described in section 3; the proportional odds models will be adjusted for the categories of the pulmonary+ outcome at baseline and for study site pharmacy. If participants in both disease severity strata are enrolled, the models will also be adjusted for the interaction between disease severity stratum and pharmacy.

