 - If Day 5 data are missing for a substantial proportion of participants (e.g., more than 5% of the mITT cohort), multiple imputation will be used to impute missing Day 5 data for the pulmonary and pulmonary+ outcomes. For the imputation, the following baseline covariates will be considered in addition to the indicator for treatment group: age, sex, country, duration of symptoms prior to enrollment, status of the ordinal pulmonary (or pulmonary+) outcome, and presence of comorbidities. Ten rounds of imputation will be used to estimate the summary odds ratio.
 - The number and proportion of participants with missing data will be reported.

Sensitivity analyses

- As sensitivity analyses, the treatment groups will be compared by **modified intentionto-treat (mITT)** after excluding participants who did not receive any of the assigned investigational agent (active or control). This mITT analysis will be provided at important decision points, e.g., when the test statistic approaches the monitoring boundary, and for the final analyses after completion of the trial.
- Treatment groups will be compared for the pulmonary and pulmonary+ outcomes on Days 1-7, to monitor the consistency of the treatment effect over time.

Assessment of model assumptions

- For the pulmonary and pulmonary+ outcomes at Day 5, the proportionality assumption
 of the odds ratio will be assessed (by including the interaction between the treatment
 group indicator and indicators for the Day 5 cumulative ordinal categories in the model,
 as well as the interactions between the treatment group indicator and the indicators for
 the strata by baseline pulmonary+ categories and site pharmacy; this corresponds to
 testing for separate slopes using a partial proportional odds model, see section 3 under
 "ordered categories"). If there is evidence for non-proportionality, the summary odds
 ratio in the proportional odds model will still be used to quantify the treatment effect, and
 the analyses of the dichotomized ordinal outcome categories will be used to help
 interpret the treatment effect.

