10.4 Interim Monitoring for Futility

After investigational agents have passed the initial futility assessment (based on the pulmonary and pulmonary+ outcomes at Day 5, assessed for the first 300 participants), further futility analyses will be based on the primary outcome of *time to sustained recovery*. The aim of these analyses will be to consider whether an investigational agent should be discontinued due to a low probability of achieving statistical significance for the primary endpoint of sustained recovery at the completion of the 90 day follow-up.

Conditional power calculations for time to sustained recovery will be presented under a range of scenarios. In the primary futility analysis, it will be assumed that the treatment effect for the

future, as yet unobserved follow-up will be as hypothesized in the study design (RRR=1.25). As secondary analysis, the treatment effect for future follow-up will be assumed to be similar to the observed effect. Additional scenarios may be provided. Typical futility guidelines recommend stopping a trial when conditional power (assuming the originally hypothesized treatment effect for the future follow-up) is below 10%-15%.¹³

As a guideline, futility will first be assessed when 50% of the planned number of sustained recoveries have occurred, and a value of 15% will be suggested as a threshold for the conditional power. An additional assessment will take place at 75% of the events. Conditional power will be computed using Gray's test with ρ =0, the competing risk analogue of the log-rank test.¹⁴

Decisions to terminate an agent for futility will include a broad assessment of the risk/benefit trade-off in addition to these guidelines.

11 Data Completeness and Study Conduct

According to the protocol, the pulmonary and pulmonary+ outcomes will be assessed on days 0-7; the decision rules for at the initial futility assessment are based on these outcomes on Day 5. The pulmonary outcome will also be assessed on Days 14 and 28. The primary outcome, "time to sustained recovery", will be assessed through Day 90. Clinical data will be collected on Days 0-7, 14, 28, 60 and 90; mortality and re-hospitalizations will be assessed through 18 months. After hospital discharge, in-person visits are scheduled on Days 1, 3, 5, 28, and 90, when blood is collected (plasma and serum); other visits may be conducted by phone (Days 7, 14, 42, 60, and 75). The data collection schedule is included in Appendix D of this SAP.

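### Imputation of missing Day 5 ordinal outcomes uses baseline covariates and arm only, although the same outcomes are scheduled daily on Days 1-7

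*SAP*

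**What the plan says.** The rule is in SAP section 10.2.2, under Missing data, for final analyses after completion of the trial. It is conditional: "If Day 5 data are missing for a substantial proportion of participants (e.g., more than 5% of the mITT cohort"). When it applies, "the following baseline covariates will be considered in addition to the indicator for treatment group: age, sex, country", followed by symptom duration, "status of the ordinal pulmonary (or pulmonary+) outcome, and presence of comorbidities". The list is introduced as baseline covariates, so the ordinal status in it is the baseline one. The next sentence fixes the number of imputations: "Ten rounds of imputation will be used to estimate the summary odds ratio".

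The same outcomes are recorded on neighbouring days. Section 11 states that "the pulmonary and pulmonary+ outcomes will be assessed on days 0-7", and Table D-1 in Appendix D marks both assessments on each of those days. The SAP uses the other days only in separate by-day comparisons: section 8.3 lists "Pulmonary+ and pulmonary ordinal outcomes on Days 1-7" as secondary outcomes, and section 10.2.2 adds, as a consistency check, that "Treatment groups will be compared for the pulmonary and pulmonary+ outcomes on Days 1-7".

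At interim analyses, including the futility review, section 10.2.2 uses only participants with observed Day 5 data and imputes nothing.

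**The concern.** Multiple imputation helps when the imputation model knows something about the missing value that the analysis model does not. Here it knows little more. Under SAP sections 3 and 10.2.2, the Day 5 proportional odds model already adjusts for baseline pulmonary+ category and site pharmacy, and pharmacy largely absorbs country. Only age, sex, symptom duration and comorbidities are new, and all are fixed at baseline.

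A Day 5 value may be missing because of what happened after baseline, for instance because the participant had improved and gone home, or had worsened. A baseline-only model then imputes as though that had not happened. A status recorded the day before or after carries most of the needed information and would make the missing-at-random assumption more credible. At stake are some precision and, in one particular circumstance, bias in the Day 5 summary odds ratio (OR).

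**Working it through.** **The plan's own figure.** The only design figure for this outcome is 95% power with 300 participants, OR 1.60, one-sided alpha 0.30 (SAP sections 1.4 and 10.2.2). Whitehead's formula for 1:1 allocation gives

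N = 12(z₀.₇₀ + z₀.₉₅)² / [(ln 1.6)²(1 − Σp̄³)] = 255.6 / (1 − Σp̄³).

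The documents reviewed do not give the control distribution. Five assumed seven-category distributions gave power of 94.4% to 96.4% at N = 300, so the stated figure is reproduced. The point below does not depend on it.

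**Trigger for MP0420.** Appendix G gives 485 infused participants. 5% × 485 = 24.25, so 25 or more missing values exceed the example threshold.

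**Precision.** The documents give no day-to-day correlations, so these are assumptions. Approximate information lost = missing fraction × (1 − R²).

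- Baseline only, correlation 0.6: R² = 0.36; at 8% missing, 0.08 × 0.64 = 5.1%.
- With Day 4, correlation 0.9: R² = 0.81; at 8% missing, 0.08 × 0.19 = 1.5%.

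This is rough and treats the baseline predictor as new information. Since the analysis already conditions on baseline category, the baseline-only loss would be nearer the full 8%. With Day 4 it would be about 0.08 × 0.19/0.64 = 2.4%, if baseline adds nothing once Day 4 is known. The direction is the same.

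Over a range of assumed category-level correlations with Day 5 (baseline 0.38 to 0.54, Day 4 0.86 to 0.91), the approximation 1/√(1 − loss) gives this standard-error inflation:

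| Missing | Baseline only | Day 4 added |
|---|---|---|
| 5% | 1.8-2.2% | 0.4-0.7% |
| 10% | 3.8-4.6% | 0.9-1.4% |

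Ten imputations are enough: relative efficiency 1/(1 + loss/10) is above 0.99 throughout.

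**Bias.** Daily status was simulated from a latent autoregressive model with seven categories and the same range of correlations, 400,000 participants and one imputation per scenario. Missingness at Day 5 was unrelated to Day 4 status, related to it equally in both arms, or related to it more strongly in one arm.

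- Unrelated, or equal in both arms: the baseline-only OR was within about 0.02 of the full-data OR in every scenario (largest gap 1.614 against 1.592).
- Different by arm, with better patients missing more often:

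| Correlations with Day 5 (baseline, Day 4) | Missing | Full data | Complete cases | Baseline-only imputation | Day 4 added |
|---|---|---|---|---|---|
| 0.38, 0.86 | 6% | 1.599 | 1.513 | 1.515 | 1.593 |
| 0.38, 0.86 | 10% | 1.631 | 1.494 | 1.492 | 1.627 |
| 0.54, 0.91 | 6% | 1.759 | 1.672 | 1.673 | 1.762 |
| 0.54, 0.91 | 10% | 1.729 | 1.590 | 1.591 | 1.721 |

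On the log scale the baseline-only loss runs from 9% (1 − ln 1.673/ln 1.759) to 18% (1 − ln 1.492/ln 1.631). In every scenario, baseline-only imputation and complete cases agreed to about 0.004: the imputation step changed almost nothing.

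**The case against.** Several points on the other side stand.

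- **Little depends on this analysis.** The rule applies only at the final analysis and only above the threshold. The documents do not report Day 5 missingness for MP0420, so it may never be used.
- **Data collection reduces the discharge problem.** Section 11 schedules Day 5 as an in-person visit after discharge, and the footnotes to Table D-1 ask for telephone contact on the study day if the visit cannot take place. Death is category 7 (Appendix A), so a participant known to have died by Day 5 needs no imputation. The 9 who withdrew consent before infusion are outside the mITT cohort (Appendix G).
- **Neighbouring values will not always exist.** For discharged participants, section 11 lists contacts on Days 1, 3, 5 and 7 but none on Days 2, 4 or 6, although Table D-1 marks assessments on those days. Anyone lost early may have neither Day 4 nor Day 5. The gains above are therefore a best case.
- **The list is not firmly closed.** Covariates are to be considered, and section 1.1 provides for blinded SAP updates before unblinding. Still, everything named is baseline, and choosing auxiliary variables after unblinding would invite avoidable discretion.

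A reader might infer that the imputed categories, and so the Day 5 OR, are biased. The documents do not support that. Bias needs missingness that depends on post-baseline status given the listed covariates, and material bias in the OR appeared only when that dependence differed by arm. No passage shows either, and blinding makes the second less likely.

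**Conclusion.** The point holds as a modest improvement to a contingent secondary analysis. As written, the imputation adds little to a complete-case analysis and cannot correct for missingness driven by status after baseline. With assumed correlations of 0.6 and 0.9 and 8% missing, about 5% of the information is lost instead of about 1.5%. Bias in the summary OR is negligible when dependence on status is the same in both arms. In the scenarios where it differed by arm, the bias was 9% to 18% of the log OR at 6% to 10% missing. All correlations and missingness mechanisms are assumptions.

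Two further inferences should be resisted. The Day 5 futility decision is not affected, because it uses observed values only. The primary endpoint, time to sustained recovery, is not affected at all. Nor is the number of imputations at fault; the weakness is in the predictor list.

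**What to change.** Amend the final-analysis paragraph under Missing data in SAP section 10.2.2 before MP0420 is unblinded. Keep the listed baseline covariates and treatment arm, and add as auxiliary variables the available Days 1-4 and 6-7 values of the same outcome, plus discharge and vital status. Collapse sparse categories where needed. Retain the baseline-only model as a sensitivity analysis.

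The cost is about one sentence in the SAP and slightly more programming. No new data collection is needed, but the benefit is limited to participants who have at least one neighbouring-day value. The downside is that some categories may have to be collapsed on days with few observations.

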10.3 Interim Monitoring Guidelines for the Primary Endpoint

This section describes the interim monitoring guidelines that apply after the investigational agent has passed the initial futility assessment (after approximately 150 participants per study arm are enrolled).

As a guideline, asymmetric boundaries will be provided to monitor the primary endpoint (time to sustained recovery) for overwhelming benefit or for harm. The trial of an investigational agent should be stopped for efficacy only if there is clear and convincing evidence of superiority

of the agent versus the pooled control group with respect to the primary outcome, time to sustained recovery. For monitoring superiority, the Lan-DeMets spending function analogue of the O'Brien-Fleming boundaries will be used, with a 1-sided 0.025 level of significance over multiple looks. For computing the Lan-DeMets boundary, the information fraction at each interim analysis will be the observed total number of sustained recoveries divided by the planned number of sustained recoveries (N=843).

The monitoring boundary for harm is asymmetric, requiring less evidence to stop for harm than for superiority; a Haybittle-Peto boundary with 2.5 SD for the first 50 participants enrolled and 2.0 SD afterwards will used as a guideline for harm. With this approach, less evidence will be required for crossing a boundary for harm than for benefit.

At each full interim review after the first 169 participants have achieved sustained recovery (20% information time), the following will be provided:

- Signed square root of the value of the test statistic for Gray's test with ρ =0, ("Z-value") comparing the investigational agent versus the control group for the primary endpoint through Day 90, plotted over information time, and the asymmetric monitoring boundaries: the O'Brien-Fleming boundary with Lan-DeMets α -spending function for superiority (one-sided test with α =0.025), and the asymmetric, Haybittle-Peto boundary for harm described above.
 - Comment: Test statistics for the primary treatment comparison will be coded such that the value of the test statistic > 0 favors the investigational agent. Thus, in case of harm, the Haybittle-Peto boundary with 2 SD of the normalized test statistic, is crossed if the Zvalue for the test statistic is below -2, irrespective of information time.

In addition to the current value of the test statistic, the corresponding values of the test statistic at the previous reviews will be plotted over information time, (1) as presented at the previous DSMB meetings, and (2) re-calculated with current data (using the cutdates of the previous reports).

History of the estimated rate ratios for time to sustained recovery with 95% CIs and p-values (by Fine-Gray's method), and normalized test statistic values and p-values for Gray's test at previous DSMB reviews, as presented, and recalculated with the current data (using the cut-date of the previous reports). The latter provides information on the influence of a possible time lag in the ascertainment of sustained recovery.

10.4 Interim Monitoring for Futility

After investigational agents have passed the initial futility assessment (based on the pulmonary and pulmonary+ outcomes at Day 5, assessed for the first 300 participants), further futility analyses will be based on the primary outcome of *time to sustained recovery*. The aim of these analyses will be to consider whether an investigational agent should be discontinued due to a low probability of achieving statistical significance for the primary endpoint of sustained recovery at the completion of the 90 day follow-up.

Conditional power calculations for time to sustained recovery will be presented under a range of scenarios. In the primary futility analysis, it will be assumed that the treatment effect for the

future, as yet unobserved follow-up will be as hypothesized in the study design (RRR=1.25). As secondary analysis, the treatment effect for future follow-up will be assumed to be similar to the observed effect. Additional scenarios may be provided. Typical futility guidelines recommend stopping a trial when conditional power (assuming the originally hypothesized treatment effect for the future follow-up) is below 10%-15%.¹³

As a guideline, futility will first be assessed when 50% of the planned number of sustained recoveries have occurred, and a value of 15% will be suggested as a threshold for the conditional power. An additional assessment will take place at 75% of the events. Conditional power will be computed using Gray's test with ρ =0, the competing risk analogue of the log-rank test.¹⁴

Decisions to terminate an agent for futility will include a broad assessment of the risk/benefit trade-off in addition to these guidelines.

11 Data Completeness and Study Conduct

According to the protocol, the pulmonary and pulmonary+ outcomes will be assessed on days 0-7; the decision rules for at the initial futility assessment are based on these outcomes on Day 5. The pulmonary outcome will also be assessed on Days 14 and 28. The primary outcome, "time to sustained recovery", will be assessed through Day 90. Clinical data will be collected on Days 0-7, 14, 28, 60 and 90; mortality and re-hospitalizations will be assessed through 18 months. After hospital discharge, in-person visits are scheduled on Days 1, 3, 5, 28, and 90, when blood is collected (plasma and serum); other visits may be conducted by phone (Days 7, 14, 42, 60, and 75). The data collection schedule is included in Appendix D of this SAP.

Data completeness and study conduct reports will be provided by treatment group (for the closed report) and pooled across treatment groups (for the open report). Data summaries for the infusion of the investigational agent on Day 0 are described in Section 6; several of those reports are also relevant for monitoring study conduct and will be included in the open report or provided to study leadership, pooled across treatment groups.

The following data summaries will be provided to assess data completeness and study conduct:

- Number and percent of participants with protocol deviations, and type of protocol deviation
- Expected and observed number (% of expected) of participants who completed visits on Days 1-7, 14, 28, 42, 60, 75, and 90.
- Expected and observed number (% of expected) of participants with known outcome status for the pulmonary and the pulmonary+ outcomes on Day 5.
- Ascertainment of the primary outcome: Expected and observed number (% of expected) of
 participants with known status of "time to sustained recovery" at days 28, 60, and 90. To
 ascertain "sustained recovery", several elements are required: vital status; the status of
 hospitalization; if discharged, the status of the residence ("home" versus other).
- Expected and observed number (% of expected) of participants with known vital status at days 5, 14, 28, 60 and 90, and at months 6, 12, and 18.

- Number and percent of participants who withdrew consent or were lost to follow-up (no contact and unknown vital status for 45+ days).
- If substantial numbers of participants are lost to follow-up (e.g., more than 10% of participants), Kaplan-Meier estimates for the cumulative proportion of participants who are lost to follow-up over time, by treatment group, will be provided (closed report only).
- Listing of participants who withdrew consent, including dates of randomization, pulmonarycategory at baseline, receipt of study treatment, date of withdrawal, and reason of withdrawal.
- Length of follow-up: Median, IQR, range
- Collection of specimens: Expected and observed number (% of expected) of participants with specimens collected as specified by the protocol, by visit.
- Expected and observed numbers of participants with local laboratory data at baseline and on Day 5.

A visit counts as "expected" if the visit window has closed or the data have been received.

12 SARS-CoV-2 Antibody, Antigen, and Viral RNA Levels

SARS-CoV-2 neutralizing antibody (nAb) levels, anti-N antibody levels, and plasma antigen levels are measured in stored plasma specimens collected at baseline (Day 0), Day 1, Day 3, and Day 5. SARS-CoV-2 RNA levels are determined from mid-turbinate nasal swabs, collected at baseline. Assays are described in Appendix F.

The statistical analyses described in this section are based on the analysis plan for antibody and antigen data for bamlanivimab (LY-CoV555), the *Addendum to Statistical Analysis Plan (Version 1.0) Therapeutics for Inpatients with COVID-19 (TICO) ACTIV-3 INSIGHT 014*, dated 14 April 2021. The current update to the SAP is further informed by the completed analyses of antibody, antigen, and viral RNA data for bamlanivimab, sotrovimab, and BRII 196/198, the first three investigational agents in TICO.¹¹

Antibody, antigen, and viral RNA levels are determined centrally, and may not be available at interim analyses. If data are available, key analyses will be included in interim reports.

